8 STUDY ASSESSMENT AND PROCEDURES

8.1 Efficacy Assessments

Primary objective: Look at microbial colonization before and after treatment.

The treatment and sampling procedures will largely follow the protocol described by Shuping et al.²⁴. Briefly, the patient will be anesthetized, and the tooth isolated with rubber dam. Chlorhexidine 2% will be used to disinfect the tooth and the rubber dam. The removal of caries and the endodontic access will be carried out by sterile high-speed carbide burs. Chlorhexidine 2% will be used to disinfect the tooth and the rubber dam one more time and bacteriological sample (S0) will be taken from the tooth surface. After initial access to the root canal orifices, a bacteriological sample will be taken from the targeted canals (S1). Sterile paper points will be placed into the canal orifices, allowed to saturate and then transferred to a vial containing reduced transport fluid (RTF). For NaOCl group, canals will be instrumented up to size 30/0.04 taper using 1.5cc of 3% NaOCl in between files. For Er,Cr:YSGG laser group, canals will be instrumented up to size 30/0.04 taper using 1.5cc of normal saline in between files, then rinse each canal with 1cc normal saline and flood the access. Then ER:Cr;YSSG laser 2780nm (Waterlase Express™, BIOLASE®) with 300µm tip (EdgePro #3, RFT 3) will be placed into the mid-root of the canal. The tip will be activated and slowly withdrawn to the orifice (1-2mm/sec) following the manufacturer settings (energy 15mJ, repetition rate 50Hz, 0% air, 0% water). When the final 30.04 taper apical size is reached, a second bacterial sample will be taken (S2). All canals in all groups will be irrigated with 5cc of 3% NaOCl with the ultrasonic irrigant activation following the standard endodontic procedure protocol. Upon completion of irrigation, a third bacterial sample will be taken (S3). Before all samplings, solutions will be removed with 5cc of sterile saline and canal content will be neutralized with 5% sodium thiosulfate solution. The remaining treatment sequences of the routine root canal therapy will be carried out after these procedures including further root-end enlargement and final routine irrigation protocol. The root canals will be dried with paper points, a medication (calcium hydroxide) will be placed and the teeth sealed with a temporary restoration. Patients will return after one week (\pm 3 days) for completion of the root filling. For both groups, the treatment procedures carried out during this investigation do not differ from the standard root canal treatment protocol with the exception of additional irrigation step with the experimental solution and the bacteriologic sampling procedures.

Treatment success determined clinically and radiographically: Radiographically, Following periapical (PAI) index by Órstavík², description of radiographic findings: 1. Normal periapical structures. 2. Small changes in the bone structure. 3. Change in the bone structure with mineral loss. 4. Periodontitis with a well-defined radiolucent area. 5. Severe periodontitis with exacerbating features. Success is defined as either complete (radiographic resolution of a periapical lesion - the radiographic sign of inflammatory processes surrounding a root tip) or incomplete healing (scar tissue formation) and failure includes uncertain healing (radiographic reduction of a periapical lesion or same lesion size) or unsatisfactory healing (increase in lesion size) as determined on the radiograph. Clinically, success is defined by the absence of pain, swelling, percussion sensitivity or sinus tracts. Clinical failure is defined as the persistent presence of any of the symptoms mentioned above. Treatment success/failure measured at the standard of care 6 month, 1 year and 2 year follow up (± 7 days) post root canal filling.

8.2 Safety and Other Assessments

The resident performing the endodontic treatment will evaluate and treatment plan the case as routinely performed through a clinical and radiographic examination of the involved teeth. At least one periapical radiograph of the involved tooth will be obtained during the consultation as routine protocol requires for every root canal treatment. In order to be eligible to participate in this study, an individual must meet all of the previously mentioned criteria (check section 5.1 and 5.2). On the day of procedure, the resident will conduct and complete the root canal treatment as standard protocol requires, including medical history review/update, clinical assessment, vital signs (blood pressure). Participants, providers and observers will wear appropriate laser protection eyewear (OD 3 or greater) whenever the laser is in use.

8.3 Adverse Events and Serious Adverse Events

8.3.1 Definition of Adverse Events (AE)

An adverse event (AE) is any untoward medical occurrence associated with the use of an intervention in humans, whether or not considered intervention related. Intercurrent illnesses or injuries should be regarded as adverse events.

A pre-existing condition should be recorded as an adverse event if the frequency, intensity or the character of the condition changes.

8.3.2 Definition of Serious Adverse Events (SAE)

Serious Adverse Events (SAE)

Adverse events are classified as serious or non-serious. A serious adverse event is any AE that, in the view of the investigator is:

- fatal
- life-threatening
- requires or prolongs hospital stay
- results in persistent or significant disability or incapacity
- a congenital anomaly or birth defect
- an important medical event when the event does not fit the other outcomes, but the event may jeopardize the patient and may require medical or surgical intervention (treatment) to prevent one of the other outcomes.
- required intervention to prevent permanent impairment or damage

Important medical events are those that may not be immediately life threatening but are clearly of major clinical significance. They may jeopardize the subject and may require intervention to prevent one of the other serious outcomes noted above. For example, drug overdose or abuse, a seizure that did not result in in-patient hospitalization, or intensive treatment of bronchospasm in an emergency department would typically be considered serious.

8.3.3 Unanticipated Adverse Device Effect (UADE)

A UADE is any serious adverse effect on health or safety, or any life-threatening problem or death caused by, or associated with, a device, if that effect, problem, or death was not previously identified in nature, severity, or degree of incidence in the investigational plan or application, or any other unanticipated serious problem associated with a device that relates to the rights, safety, or welfare of subjects.

8.3.4 Classification of an Adverse Event

8.3.4.1 Severity of Event

For adverse events (AEs) not included in the protocol defined grading system, the following guidelines will be used to describe severity.

- Mild – Events require minimal or no treatment and do not interfere with the participant’s daily activities.
- Moderate – Events result in a low level of inconvenience or concern with the therapeutic measures. Moderate events may cause some interference with functioning.
- Severe – Events interrupt a participant’s usual daily activity and may require systemic drug therapy or other treatment. Severe events are usually potentially life-threatening or incapacitating. Of note, the term “severe” does not necessarily equate to “serious”.

8.3.4.2 Relationship to Study Intervention

All adverse events (AEs) must have their relationship to laser assessed by the clinician who examines and evaluates the participant based on temporal relationship and his/her clinical judgment. The degree of certainty about causality will be graded using the categories below. In a clinical trial, the study product must always be considered.

- Related – The AE is known to occur with the laser, there is a reasonable possibility that the laser caused the AE, or there is a temporal relationship between the laser and event. Reasonable possibility means that there is evidence to suggest a causal relationship between the laser and the AE.
- Not Related – There is not a reasonable possibility that the administration of the laser caused the event, there is no temporal relationship between the laser and event onset, or an alternate etiology has been established.

OR

- Definitely Related – There is clear evidence to suggest a causal relationship, and other possible contributing factors can be ruled out. The clinical event, including an abnormal laboratory test result, occurs in a plausible time relationship to laser administration and cannot be explained by concurrent disease or other drugs or chemicals. The response to withdrawal of the laser group (dechallenge) should be clinically plausible. The event must be pharmacologically or phenomenologically definitive, with use of a satisfactory rechallenge procedure if necessary.
- Probably Related – There is evidence to suggest a causal relationship, and the influence of other factors is unlikely. The clinical event, including an abnormal laboratory test result, occurs within a reasonable time after administration of the laser, is unlikely to be attributed to concurrent disease or other drugs or chemicals, and follows a clinically reasonable

response on withdrawal (dechallenge). Rechallenge information is not required to fulfill this definition.

- Possibly Related – There is some evidence to suggest a causal relationship (e.g., the event occurred within a reasonable time after administration of the laser). However, other factors may have contributed to the event (e.g., the participant's clinical condition, other concomitant events). Although an AE may rate only as "possibly related" soon after discovery, it can be flagged as requiring more information and later be upgraded to "probably related" or "definitely related", as appropriate.
- Unlikely to be related – A clinical event, including an abnormal laboratory test result, whose temporal relationship to laser administration makes a causal relationship improbable (e.g., the event did not occur within a reasonable time after administration of the laser) and in which other drugs or chemicals or underlying disease provides plausible explanations (e.g., the participant's clinical condition, other concomitant treatments).
- Unrelated – The AE is completely independent of laser administration, and/or evidence exists that the event is definitely related to another etiology. There must be an alternative, definitive etiology documented by the clinician.

8.3.4.3 *Expectedness*

Expected adverse events include those that are expected as part of routine root canal treatment such as: the possibility of instruments breaking within the canals; perforations (extra opening) of the crown or root of the tooth; damage to existing fillings, crown or bridges; fractures of the tooth; discomfort; jaw muscle cramps and spasms; temporomandibular (jaw) joint difficulty; swelling and pain. During and after the treatment, complications may be discovered which make treatment impossible or which may require endodontic surgery or extraction of the tooth. Complications that anesthesia, injection, prescribed analgesics (pain relievers) may include, but are not limited to: swelling, infection, bleeding, discoloration of the face, discomfort, pain, nausea, drowsiness, allergic reactions, numbness or tingling of the lip, gum, or tongue (this condition is usually temporary).

A separate consent form explaining all expected adverse events for patients participating in the study will be discussed and signed by each participant (*attachment 5*). Waterlase Express™: Water from spray may splash during laser use. This device do involve Class IV lasers that can harm eyes. Participants, providers and observers will wear appropriate laser protection eyewear (OD 3 or greater) whenever the laser is in use. No other known risks are expected when using Waterlase Express™ for root canal disinfection (*attachment 3*).

Investigator will be responsible for determining whether an adverse event (AE) is expected or unexpected. An AE will be considered unexpected if the nature, severity, or frequency of the event is not consistent with the risk information previously described.

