The laser has been used with importance in most medical and dental specialties, especially in Endodontics in the last decade. Its properties are known in the incision of tissues, in cases of pulpotomy, and reduction of postoperative pain. Regarding the use inside the root canal, there are still some doubts about its effectiveness. Lasers, regardless of types, are individually unable to eliminate contaminations in the root canal since the root canal temperature will reach the limit to where damage to adjacent tissues and nerves occurs before bacteria are ablated¹⁷. In order for lasers to ablate all contaminants in the root canal, the absorption efficiency of laser energy at the root canal surface has to increase greatly at lower laser power without substantially raising the temperature in the root canal. Due to the high affinity of water with Erbium laser, different Erbium family lasers (Er:YAG 2940nm and Er,Cr:YSGG 2780nm) represent the cutting-edge technology for laser-activated irrigant (LAI) in Endodontics. These two wavelengths are the most appropriate for different irrigant solutions, considered safe and respecting accepted clinical parameters¹⁸.

An FDA cleared ER:Cr;YSSG laser machine (Waterlase Express™, BIOLASE®) will be tested (*clearance number: K161669, attachment 2*). This machine has different settings which are clinically suitable to be used in root canal disinfection protocols. Many studies have been published to test the efficacy of ER:Cr;YSSG laser in biofilm removal inside the root canal system¹⁹. Qualitative and quantitative *in vitro* studies showed that ER:Cr;YSSG laser activation of 4% NaOCl resulted in greater *E. faecalis* biofilm reduction within the dentinal tubules²⁰, and improved antimicrobial effect of NaOCl in comparison to syringe irrigation²¹. One blind randomized clinical trial concluded that ER:Cr;YSSG laser can achieve promising endodontic outcome, however larger sample size with longer follow-up periods are needed²². This study is to validate the method of using (Waterlase Express™, BIOLASE®) to ablate or disinfect microbe contaminants, and achieve cleaning of the root canal in association with standard endodontic procedures.

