Proof-of-concept experiments in endodontic treatment could open the door for laser to be used in numerous clinical anti-biofilm applications. The assessment of bacterial reduction during endodontic therapy by bacterial sampling and culturing is an established technique and has been used to evaluate treatment protocols or variations thereof²³⁻²⁶. There is a current need for a better disinfecting agent that is capable of overcoming the limitations of the currently used irrigation solutions.

Based on our preliminary findings, testing local single topical application of a very low dose of Er,Cr:YSGG 2780nm (Waterlase Express™, BIOLASE®) has a potential as an advanced anti-biofilm clinical therapy with its potent antibacterial and anti-biofilm activities.

The purpose of this study is to develop an irrigation disinfection protocol for eradicating biofilms with a clinically approved and commercially available Er,Cr:YSGG 2780nm laser. This protocol will be testing local application of (Waterlase Express™, BIOLASE®), within the root canal system in patients going through routine endodontic treatment, will evaluate its potential as an advanced anti-biofilm disinfection technique and compare it to other currently used antibacterial protocols.

2.2.1 *Pharmacokinetics, Pharmacodynamics and Toxicology*

N/A

2.2.2 *Assessment for Potential Study Products Drug-Drug, Drug-Device, Device-Device Interactions*

N/A

2.2.3 *Clinical Adverse Event Profile*

There are no known adverse effects associated with the (Waterlase Express™, BIOLASE®) device being used in this study. The Waterlase Express™ device complies with Industry Canada license-exempt RSS standard(s) and installed, operated, and maintained according to the current revision of the guidelines specified in the Canadian standard CAN/CSA-Z386:2014 safe use of lasers in health care. It also complies with FDA laser standards. All these light sources have been independently tested by regulatory authorities and used both clinically and experimentally for over a decade. Since the device is Class IV laser, participants, providers and observers will wear appropriate laser protection eyewear (OD 3 or greater) for the 2780 nm wavelength whenever the laser is in use.

2.2.4 *Dosing Rationale*

Tip: RFT3, 15mJ 50Hz 0.75W 0% air 0% water, according to manufacturer instructions (attachment 3).

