2.3 Risk/Benefit Assessment

2.3.1 *Known Potential Risks*

Only the risks or discomforts that can arise during or after any routine root canal treatment procedure apply. Bacterial sampling will not have any adverse effect on the treatment or on treatment outcome. There are no potential risks expected from the noninvasive bacteriological

sampling, including any potential physical, psychological, social, economic, monetary, legal or other risks. Identifying the antibacterial benefits of Er,Cr:YSGG laser is the goal of our experiment.

Er,Cr:YSGG laser has been used in dentistry as an alternative technology to overcome the limitations of current chemical-mechanical instrumentation techniques and improve root canal disinfection. Er,Cr:YSGG laser used in this experiment is limited within the root canal system and applied on dentine surfaces only. It will not be used systemically. 300µm laser tip will be kept within the root canal system, placed into the mid-root of the canal. The tip will be activated and slowly withdrawn to the orifice (1-2mm/sec) following the manufacturer settings as proposed in this protocol. Experiment was designed that the final root canal disinfection is not relying on be irrigated with 5cc of 3% NaOCl with the ultrasonic irrigant activation following the standard endodontic procedure protocol and then antibacterial medication (CaOH₂) will placed as done routinely to treat cases with pulp necrosis and apical periodontitis.

Provider, patient and assistant will wear appropriate laser protection eyewear for the 2780 nm wavelength (OD 3 or greater) whenever the laser is in use.

Data that will be collected include: demographic data, medical history/medications, tooth number, diagnosis and the PDM chart number (for potential verification of study correctness). All treatment procedures at the PDM, including the routine root canal treatment of the participants, during which the samples will be taken, are subject to strict HIPPA (privacy) and OSHA (hygiene) regulations.

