2.3.3 Assessment of Potential Risks and Benefits

The risks or discomforts that can arise during or after any routine root canal treatment procedure apply. All subjects will receive the same standard of care disinfection protocol, with one arm receiving the additional Waterlase Express™ laser. However, this device do involve Class IV lasers that can harm eyes. Participants, providers and observers will wear appropriate laser protection eyewear (OD 3 or greater) whenever the laser is in use. Our consent forms (for routine root canal procedures and for the study) contain clinic and investigator contact information (*attachment 4 and 5*). Subjects' concerns or complaints will be reviewed routinely.

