8.3.6 Adverse Event Reporting

Reporting Period

Adverse events will be reported from the time of informed consent until study completion.

Investigator Reporting: Notifying the Study Sponsor

N/A

Investigator Reporting: Local Reporting Requirements

The investigator will report AEs and SAEs to the IRB/EC of record and other local regulatory groups per the local requirements.

New information regarding the SAE will be reported as it becomes available and in the same manner that the initial SAE (i.e. SAE form). The investigator will follow the event to resolution or until the event is deemed and documented irreversible, whichever is longer.

8.3.7 *Serious Adverse Event Reporting*

The study investigator shall complete an Unanticipated Adverse Device Effect Form and submit to the reviewing Institutional Review Board (IRB) . The study investigator is responsible for conducting an evaluation of an unanticipated adverse device effect and shall report the results of such evaluation to the Food and Drug Administration (FDA) and to all reviewing IRBs and participating investigators per the applicable regulation.

8.3.8 *Reporting Events to Participants*

N/A

8.3.9 *Events of Special Interest*

N/A

8.3.10 *Reporting of Pregnancy*

Pregnancy, in and of itself, is not regarded as an AE unless there is suspicion that study device or process may have interfered with the effectiveness of a contraceptive medication or method. When a pregnancy has been confirmed in a subject, and the fetus is exposed to study device and/or process (maternally or paternally), the following procedures should be followed to ensure subject safety:

Data on fetal outcome are collected for regulatory reporting and device safety evaluation. Follow-up should be conducted for each pregnancy to determine outcome, including spontaneous or voluntary termination, details of the birth, and the presence or absence of any birth defects, congenital abnormalities, or maternal and/or newborn complications.

8.4 *Unanticipated Problems*

8.4.1 *Definition of Unanticipated Problems (UP)*

The Office for Human Research Protections (OHRP) considers unanticipated problems involving risks to participants or others to include, in general, any incident, experience, or outcome that meets all the following criteria:

- Unexpected in terms of nature, severity, or frequency given (a) the research procedures that are described in the protocol-related documents, such as the Institutional Review Board

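### The heat hazard named in the background is not carried into the risk and expectedness sections, so a laser heat injury not recognised as such could be coded as an expected routine event

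*Combined protocol and SAP*

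**What the plan says.** Section 2.2 (Background) says of in-canal lasers of all types that "the root canal temperature will reach the limit to where damage to adjacent tissues and nerves occurs before bacteria are ablated". It then says that more energy must be absorbed at lower power without a large rise in temperature. It describes the two erbium wavelengths, one of which is the study laser's, as "considered safe and respecting accepted clinical parameters".

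The later sections describe risk as follows:

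- 2.2.3 (Clinical Adverse Event Profile): "There are no known adverse effects associated with the (Waterlase Express™, BIOLASE®) device being used in this study".
- 2.3.1 (Known Potential Risks): "Only the risks or discomforts that can arise during or after any routine root canal treatment procedure apply".
- 2.3.3 (Assessment of Potential Risks and Benefits) adds only that "this device do involve Class IV lasers that can harm eyes".
- 8.3.4.3 (Expectedness) lists water splash and eye harm for the device, followed by "No other known risks are expected when using Waterlase Express™ for root canal disinfection".
- 8.3.9, headed "Events of Special Interest", is marked N/A.

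The list of expected events in 8.3.4.3 includes swelling and pain as part of root canal treatment. Among the complications of anaesthesia, injection and analgesics it includes "numbness or tingling of the lip, gum, or tongue (this condition is usually temporary".

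**The concern.** The protocol names a specific harm from lasers in the canal and then tells investigators that the device has no known risk beyond splash and eye exposure. An investigator working from the risk and expectedness sections has no prompt to consider heat when a participant reports pain, swelling or altered sensation, and each of those already has a routine explanation on the expected list.

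Expectedness matters for reporting. Under 8.4.1 an unanticipated problem must meet every criterion, including being unexpected. An event coded as expected therefore drops out of that route, even if someone later rates it as related to the laser. It would then sit among routine post-operative events, and the safety analysis in 9.4.4 has no step that would bring an excess in the laser arm to light.

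**Working it through.** No arithmetic bears on this point. The check is to set the sections side by side and follow a heat injury through the rules.

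**1. Is the hazard carried forward?** 2.2 names heat damage to adjacent tissue and nerves. Sections 2.2.3, 2.3.1, 2.3.3 and 8.3.4.3 do not mention heat, and three of the four contain a sentence that excludes further device risk (2.2.3, 2.3.1, 8.3.4.3). The device text in 8.3.4.3 also does not match this trial's use: it lists splash from the water spray, while 2.2.4 and 4.3 give the setting as 0% water. Those passages need to be reconciled as well.

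**2. A heat injury recognised as such.** Under 8.3.4.3 an event is unexpected if its nature, severity or frequency does not fit the risks described. Thermal injury is not on the list, so its nature does not fit and it is unexpected. If serious, it could also meet the definition of an unanticipated adverse device effect in 8.3.3.

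**3. A heat injury not recognised as such.** Suppose it is recorded as pain, swelling or numbness.

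- *Nature:* the symptom is on the expected list, so the nature test in 8.3.4.3 is met.
- *Severity and frequency:* the list gives no grades or rates. The only guide is that numbness is usually temporary, so persisting numbness could still count as unexpected, but pain and swelling have no such marker.
- *Second rule:* 8.3.5 restates expectedness by severity and/or frequency and omits nature, the element best able to separate a heat injury from routine events. The two rules differ.
- *Ascertainment:* 8.3.5 seeks events by non-directive questioning and, as appropriate, by examination. Nothing asks about heat injury or persisting sensory change.
- *Causality:* 8.3.4.2 requires every event to be rated for its relationship to the laser. It leaves two alternative scales joined by OR. On the two-level scale, an established alternative cause is enough for a rating of not related, and anaesthesia can readily appear to supply one for numbness.

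Such an event can therefore end as expected and not related.

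**4. Would the analysis find it?** 9.4.4 (Safety Analyses) repeats the colony-count endpoint and the routine examination text. It plans no tabulation or comparison of adverse events by arm.

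**The case against.** The strongest reply is that the safety rules are better than the risk text. Events are to be recorded as diagnoses where possible (8.3.5). Every event gets a laser-causality rating separate from expectedness, and a temporal relationship alone can support a rating of related (8.3.4.2). The Schedule of Activities has adverse-event review, clinical assessment and imaging at all five visits, and pain is scored at 4, 24 and 48 hours. These safeguards stand, and they narrow the problem to injuries whose cause is not recognised. They do not remove it: a diagnosis is recorded only if someone thinks of it, and the risk text discourages that.

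A second reply is that the background sentence concerns a laser used alone and pursued until bacteria are ablated. The same section calls the erbium wavelengths safe with irrigants. The access is flooded with saline before firing (4.1), the tip goes only to mid-root (2.3.1), and 15 mJ x 50 Hz = 0.75 W lies low in the device's 0.1 to 4.0 W range (6.1.1). This is fair, and nothing here shows that the laser as used is unsafe. But it is an argument for why the hazard may be small, and the risk sections do not make it. The dosing rationale (2.2.4, 4.3) gives settings and refers to manufacturer instructions, with no temperature figure in the protocol. The attachment cited there was not available.

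A reader might go further and infer that any laser heat injury would be filed as expected, or that the protocol denies the hazard. The documents do not support either. A recognised injury is unexpected under 8.3.4.3, and N/A in 8.3.9 defines no special-interest event; it makes no statement about heat. Nor can it be said that the consent form omits the hazard, since its text was not available to check.

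**Conclusion.** The inconsistency between 2.2 and the risk and expectedness sections is on the page and should be corrected. Its consequence is limited: a heat injury has no stated classification, and one that presents only as listed symptoms and is not recognised could be coded as expected and go unnoticed in the analysis.

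Severity is moderate. The documents give no rate of heat injury or of misclassification, so the size cannot be put as a number. A zero-event confidence bound for the laser arm or an energy-per-length calculation would not measure this defect.

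The conclusion assumes that investigators classify from the protocol text as written and that the attachments not available here (device instructions, consent form) do not already address heat injury.

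**What to change.** 1. Reconcile 2.2.3, 2.3.1, 2.3.3 and 8.3.4.3 with 2.2, stating the heat hazard together with the reasons for thinking it small. Reconcile the spray-splash text with the 0% water setting. Check the consent form against the result.
2. Use one expectedness test: align 8.3.5 with 8.3.4.3, so that nature, severity and frequency all count.
3. In 8.3.9, replace N/A with *suspected thermal injury of adjacent tissue, or sensory change persisting after the anaesthetic has worn off*.
4. Ask about it in both arms at the adverse-event reviews already scheduled, and tabulate it by arm in 9.4.4.
5. State that neither the routine list nor the new risk wording makes such an event expected or removes it from unanticipated-problem or adverse-device-effect reporting. Without this sentence, step 1 could backfire: listing heat damage would make it a described risk under 8.3.4.3 and a previously identified effect under 8.3.3.

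The cost is protocol wording, consent wording if the check calls for it, one line on the adverse-event form, one table, and a slightly less favourable risk statement. No change to laser settings or to care is proposed.
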